The study will be monitored by personnel specifically contracted from a company external to the promoter, and an in-person visit will be made at the start, an intermediate visit, and a final visit at each participating center. At the beginning of the study, the first visit will be made, during which all aspects of the study will be explained to the research staff, the informed consent procedure will be explained, the protocol will be reviewed, the way in which patient data will be collected, the responsibilities of the researcher, the dispensing and maintenance of the samples and all related issues. Telephone follow-up will be provided to the centers throughout the duration of the study.

The monitor will have access to both paper and computerized medical records and will ensure that patient data are properly collected and stored in the investigator's file for the time required by current regulations.

The monitor will be informed of adverse events occurring during the clinical investigation through the investigator at each center and will report serious and related events to the authorities within the established time limits.

Evaluation	Visit 1 Basal	Visit 2	Visit 3 End of washing	Visit 4 EMC or EME	Visit 5. End of washing	Visit 6 EMC or EME	Visita 7
DAY of the study	-3 *	-2	0	5	7	12	40±2
Selection Criteria Evaluation	X						
Explanation of study and signature of consent	X						
Clinical data collection	X						
Randomization		X					
VAS	X			X		X	X

Oswestry Questionnaire	X			X		X	x
Temporary electrode implant without stimulus		X					
Start of spinal cord stimulation according to randomization A or B (day 3)			X		X		
System tolerability		X	X	X	X	X	
Adverse effects		X	X	X	X	X	x
Subsequent follow-up							x

(*) window of -2 days with respect to Visit 3.

A.7 STATISTICAL CONSIDERATIONS

This is a multicenter, controlled, randomized (spinal cord stimulation method: EMC or EME), crossover and single-blind study.

First, a descriptive analysis of the study variables will be performed, calculating the absolute and percentage frequency (n and %) of each category in the qualitative variables; in the quantitative variables, we will first study whether they fit the Gaussian distribution by applying the Kolmogorv-Smirnov goodness-of-fit test to the "Normal" distribution, showing the means and standard deviations if yes, and the medians and 25th and 75th percentiles if no, and if no, the medians and 25th and 75th percentiles.

In order to respond to the main objective of the study, two variables will be calculated for each patient that reflect the difference between the initial VAS minus the final VAS, one for each type of stimulation (EMC or EME). We will calculate whether these differences conform to the Gaussian distribution. If they fit the "Normal" distribution, the means with their standard deviations will be calculated for each of them, with the Student's t-test for paired samples to study if this difference is statistically significant, these means will be adjusted for age and sex, establishing the possible statistical differences with a general linear model of repeated measures. In the case of not obtaining distributions that fit the "Normal", the medians and the 25th and 75th percentiles will be calculated, obtaining the possible statistical differences by applying the Wilcoxon test.

For the objective of estimating the proportion of patients with a minimum decrease of 50%, it will be calculated in each case which patients meet this condition, calculating the percentage of patients in each type of stimulation, and studying the possible statistically significant differences with the Mc Nemar test.

The disability associated with pain will be evaluated with the descriptive statistics already mentioned and for each moment of the study and in each type of stimulation.

Variables will be created with the differences between the initial and final quality of life scores, studying their differences with the same parameters and tests discussed for the differences in VAS.

The absolute and relative frequencies (%) of each of the adverse effects found in the follow-up will be calculated as a safety study, in the total of the study and for each type of stimulus. Possible differences will be studied with the Mc. Nemar test.

A statistical significance level of $p < 0.05$ is considered, thus establishing a safety level of 95%.

All analyses will be performed with SPSS software version 24.0 (IBM Corp. Released 2016. IBM SPSS Statistics for Windows, Version 24.0. Armonk, NY: IBM Corp.)

Sample size

The main objective of the study is to establish a mean difference in the decrease in VAS. Based on this, we estimate a difference between the two methods of spinal cord stimulation (EMC and EME) of 1.9 points, in agreement with previous data in the medical literature,⁵⁵ with standard deviation of 3.2 and 2.0, assuming a Spearman correlation between both values of 0.5 (minimum). Using the formula for paired mean difference, for a confidence level of 95% and a statistical power of 80%, 19 patients who meet the inclusion criteria and do not meet any exclusion criteria are required, calculating a loss rate of 20%, 24 patients are expected to be included in the study.

A.8 DATA MANAGEMENT

A clinical research data collection form (CRF) will be created, where each investigator will collect the data of each patient participating in the study.

In agreement with the scientific committee, minimum and maximum values will be established for each variable of the CRF, creating validation rules and messages to the user communicating the validation rule that is not being complied with, as well as input masks for the variables that require it, such as dates. It will be possible to proceed to fill the CRF in successive times, with the consequent saving at each moment.

A.9 AMENDMENTS

The Investigational Product, Protocol, CRF, informed consent or other subject information, or other clinical investigation documents may be amended during the clinical investigation if necessary. In this case a justification statement will be included with each amended section of a document. Proposed amendments to the Protocol will be agreed between the sponsor and the coordinating investigator. They should be notified to and approved by the CEIM and regulatory authorities if required and the version number and date of the amendments will be documented.

For non-substantive changes that do not affect the rights, safety, and welfare of human subjects and are not related to the objectives or endpoints of the clinical investigation, notification to CEIM and, where appropriate, to regulatory authorities will be sufficient.

A.10 DEVIATIONS FROM THE CLINICAL RESEARCH PLAN

Reports of deviations will be communicated to CEIM, if the deviation affects the rights, safety and welfare of the subjects or the scientific integrity of the clinical investigation. In such cases, written approval will be obtained from CEIM.

In emergency circumstances, deviations from the protocol to protect the rights, safety, and welfare of human subjects may proceed without prior approval of the sponsor and the CEIM. Such deviations should be documented and notified to the sponsor and CEIM as soon as possible.

A.11 PRODUCT ACCOUNTING

Access to investigational products will be controlled and used only in clinical research and in accordance with the protocol.

The sponsor will maintain records to document the physical location of investigational products from the time they are shipped to participating sites until they are returned or disposed of.

The principal investigator or an authorized designee should maintain records documenting the receipt, use, return, and disposal of investigational products. Such records shall include: date received, product identification, expiration and use date, subject identification, withdrawal date if applicable, and return date for products that were not used or expired.

A.12 COMPLIANCE STATEMENT

The clinical investigation will be carried out in accordance with the ethical principles set forth in the Declaration of Helsinki, will be conducted in compliance with this standard and any regional or national regulations as appropriate.

The clinical investigation will commence when the favorable opinion of the CEIM and the authorization of the AEMPS have been obtained as well as having fulfilled any additional requirements imposed.

It will have a civil liability insurance that guarantees the Promoter's Civil Liability derived from the clinical research, for the damages caused to the participating participants that fulfills the legal requirements established in the Spanish legislation. In addition, the Civil Liability of the investigator and his collaborators and of the Owner of each hospital where it is carried out is also covered.

A.13 INFORMED CONSENT PROCESS

Informed consent must be obtained from the participant in writing prior to any specific clinical research procedure, except when special circumstances apply. The principal

investigator or his/her assigned collaborator is responsible for the process of obtaining consent.

It should contain all aspects of the clinical investigation that are relevant to the subject's decision to participate. It should avoid any coercion or undue inappropriate influences or inducements on the participant to participate. Do not disregard or appear to disregard the legal rights of the subjects. Use the subject's own language in clear and understandable terms.

The subject will be provided sufficient time to read and understand the informed consent form and consider participation in the clinical investigation. It will include the dated handwritten signatures of the subject and the principal investigator or his/her authorized designee responsible for executing the informed consent process. The subject will be provided with a copy of the signed and dated form and any other written information.

Special circumstances for informed consent are as follows.

- Subjects who need legally authorized representatives. The legally authorized representative can give informed consent only if a subject is incapable of making the decision to participate and, the subject must also be informed about the clinical investigation to the extent of his or her capacity to understand.
- Subject unable to read or write: must be obtained using a supervised oral process, an independent witness must be present during the process. It should be read aloud and explained to the prospective subject or his or her legally authorized representative, and whenever possible, either should personally sign and date the form. The witness also personally signs and dates the form attesting that the information was accurately explained and that consent was freely given.
- Urgent treatments: Urgent treatments are not foreseen but if this is the case, if the patient's prior consent is not possible due to the patient's medical condition, the signature of his/her legally authorized representative will be requested. The participant or his/her legally authorized representative will be informed as soon as possible and will be asked to give consent as soon as his/her condition permits.

A.14 ADVERSE EVENTS, ADVERSE EFFECTS OF THE PRODUCT AND PRODUCT DEFICIENCIES

Definitions

Adverse Event (AE)

An adverse event (AE) is any unintended medical episode, unanticipated illness or injury, or any clinical sign, including an abnormal laboratory finding, in subjects, users, or any other person, whether or not related to the investigational product. Includes medical device or control; includes events related to the procedures used.

Serious Adverse Event (SAE)

Any adverse event that:

- Leads to death
- Serious deterioration in health status that results in:
 1. produced a life-threatening illness or injury;
 2. Permanent damage to bodily structure or function
 3. Requires hospitalization or prolongation of hospitalization
 4. Unplanned medical/surgical intervention to avoid treatment or life-long injury to a bodily structure or function.
- Results in fetal damage, congenital anomaly or birth defect.

For reporting purposes, adverse events that are considered medically significant, even if they do not meet the above criteria, such as those that put the patient at risk or require intervention to prevent any of the above outcomes, will also be treated as serious.

Adverse Device Event (ADE)

An adverse event related to the use of an investigational medical device. This definition includes adverse events resulting from insufficient or inadequate instructions for use, deployment, implantation, installation, or any malfunction of the investigational medical device. It includes any adverse event resulting from an error in the use of the investigational medical device.

Serious Adverse Device Event (ADE)

An adverse event of the product that has produced any consequence characteristic of a serious adverse event.

Unexpected serious adverse device event (USADE)

It is an adverse event of the product that due to its nature, incidence, intensity or consequence has not been identified in the updated version of the risk analysis report.

Product deficiencies

All deficiencies of a medical device related to: identity, quality, durability, reliability, safety/performance, malfunction/error of use, inadequate labeling.

Noticeable events

They are any AGEs; any deficiency of a medical device that could have led to an AGE if timely action had not been taken, no intervention had been made, or in less fortunate circumstances; or new findings and updates on reported events.

Expedited notification

The sponsor will notify the AEMPS of all serious adverse events whether they are related to the investigational medical device or not, whether they occur in Spain or in other states and whether they have occurred in the authorized clinical investigation or in other clinical investigations or in a different context of use, provided that such medical devices are not marketed in Spain.

For marketed products, including the medical device used as a control, the requirements of the European system of vigilance of medical devices will be taken into account in order to avoid possible duplications in the notification.

Expedited Notification Deadlines

The maximum notification period will be 15 calendar days from the moment the sponsor became aware of the serious adverse event. When the serious adverse event has caused the death of the subject, or endangered his life, the sponsor shall inform the AEMPS within a maximum of 7 calendar days from the moment the sponsor became aware of the case. Such information should be completed, as far as possible, within the following 8 days.

Recording and reporting of adverse events and incidents

All adverse events and incidents occurring from the inclusion of the patient in the study (i.e., from the signing of the consent form) until the end of the planned follow-up per patient should be recorded in the CRF by the investigator noting their characteristics. All adverse events should be recorded using medical terminology.

Procedures for reporting serious and unexpected adverse events and adverse incidents.

All serious adverse events and adverse incidents should be reported to the sponsor's safety committee. This will include, but is not limited to

- Death from any cause
- Life-threatening hemorrhage
- Intracranial hemorrhage
- Epidural hematoma
- Meningitis
- Cerebrovascular accident
- Deep thrombocytopenia (platelet count <50,000/mm³)

Any adverse and/or unexpected AAG and incident should be reported to the sponsor's designated CRO (TRIDE) within 24 working hours of knowledge of the event. All information related to SAEs will be reported by e-mail using the SAE and adverse event forms of the CRD of the investigation, which must be signed by the investigator himself or a collaborating member of his team.

To report an incident, it is necessary that it is associated with a medical device or with the information provided with the medical device and that the incident is such that it has resulted in death or serious deterioration in health, or that if it occurs again it could cause them.

The types of adverse incidents that should be reported are as follows:

1. Those that result in death
2. Those resulting in serious deterioration of the patient's, user's or other person's health status, such as:
 - Life-threatening illness or injury

- Permanent impairment of a bodily function or permanent damage to a bodily structure.
 - A process that requires medical or surgical intervention to prevent permanent impairment of a bodily function or permanent damage to a bodily structure.
3. Potential incidents, which are those that could have resulted in death or serious deterioration of health, but which have not occurred due either to fortunate circumstances or to the intervention of healthcare personnel.

Incidents involving medical devices should be reported to the medical device vigilance point of the Autonomous Community. The communication should be made as soon as possible. It can be done by fax or by post. In the case of very serious incidents, it should be done as quickly as possible, by fax, until the means are available to send the communication "on line"; if fax is not available, it can be notified by telephone, sending the form by post afterwards. The form available in the CRF shall be used for this purpose.

A.15 VULNERABLE POPULATION

The clinical research will be carried out in participants whose diagnosis leads to an indication to receive the treatment under study within the general population and the inclusion of vulnerable population is not contemplated.

A.16 SUSPENSION OR EARLY DISCONTINUATION OF CLINICAL RESEARCH

The sponsor may suspend or terminate early either a clinical investigation at an individual investigational site or the entire clinical investigation for significant and documented reasons.

The national coordinator, a principal investigator, IRB/IEC or regulatory authority may suspend or terminate participation in the clinical investigation at the investigational sites for which it is responsible.

If suspicion of unacceptable risk to subjects arises during the clinical investigation, or when instructed to do so by the IRB/IEC or regulatory authority, the sponsor should suspend the clinical investigation while the risk is being determined. The sponsor should discontinue the clinical investigation if an unacceptable risk is confirmed.

The sponsor should consider discontinuing or suspending the participation of an investigational site or an individual investigator if monitoring or auditing identifies serious or repeated deviations by an investigator.

If suspension or early discontinuation occurs, the party so disposing should justify its decision in writing and promptly inform the other parties with whom it is in direct communication. The principal investigator and sponsor should keep each other informed of any communication received from either the CEIM or the regulatory authority.

If, for any reason, the sponsor suspends or discontinues research at an individual investigational site early, the sponsor should inform the responsible regulatory authority as appropriate and ensure that the principal investigator or sponsor notifies the CEIM. If the suspension or early discontinuation was in the interest of safety, the sponsor should inform all other principal investigators.

If suspension or early discontinuation occurs, the sponsor should remain responsible for providing the resources to fulfill the obligations of the protocol and existing agreements for follow-up of the subjects included in the clinical investigation and the principal

investigator or his authorized designee should promptly inform the subjects included at his investigational site, if appropriate. The method and timing of this communication will depend on the circumstances and perceived risks.

When the sponsor concludes an analysis of the reason for suspension, implements the necessary corrective actions, and decides to lift the temporary suspension, the sponsor should inform the principal investigators, the IRB/IECs, and, where appropriate, the regulatory authorities of the justification and provide them with the relevant data supporting this decision. The concurrence of the IRB/IEC and, where appropriate, the regulatory authorities should be obtained prior to resumption of the clinical investigation. If the subjects have been informed of the suspension, the principal investigator or his/her authorized designee should inform them of the reasons for resumption.

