The present study is aimed at a population of patients with postlaminectomy syndrome after back surgery. The inclusion and exclusion criteria are described below.

Inclusion criteria

1. Patients over 18 years of age.
2. Patients with FBSS syndrome with leg pain or leg and back pain.
3. Obtain a VAS score ≥ 7 .
4. Having received pharmacological medical treatment for at least 6 months after back surgery.
5. The patient has signed the informed consent form.

Exclusion criteria

1. Patients under 18 years of age.
2. Patients requiring any diathermic energy source (microwaves, ultrasound or short wave).
3. Patients with a pacemaker.
4. Patients with a defibrillator.
5. Patients with a cochlear implant.
6. Patients with other active implanted devices.
7. Patients who are scheduled to undergo any of the following procedures during the duration of the study: magnetic resonance imaging, defibrillation or cardioversion, electrocautery, lithotripsy, radiofrequency or microwave ablation and any other high-frequency ultrasound procedure,
8. Women of childbearing age who are not using an adequate contraceptive method.
9. Pregnant or lactating women.
10. Participation in another trial.
11. Patients who have expressed their desire not to participate in the study and have not formed the informed consent form.
12. Patients with a previous failed spinal cord stimulation implant.

Number of participants

Twenty-four subjects will be selected who meet the inclusion criteria and do not meet any exclusion criteria, calculating a loss rate of 15%-20%³⁶. 19-20 patients are expected to be included in the study.

Duration of clinical research

A total duration of 18 months plus an additional 6 months to submit the final report is foreseen, with the following schedule for the study:

Start of the study: planned for July 2018 To be determined based on deadlines.

Inclusion period: 16 months, until November 2019.

Follow-up period: planned until January 2020.

Analysis and report: expected in July 2020.

Valuation criteria

The primary endpoint is the variation in VAS between the end of EMC mode and EME mode.

STUDY OUTLINE

Evaluation	Visit 1 Basal	Visit 2	Visit 3 End of washing	Visit 4 EMC or EME	Visit 5. End of washing	Visit 6 EMC or EME	Visita 7
DAY of the study	-3 *	-2	0	5	7	12	40±2
Selection Criteria Evaluation	X						
Explanation of study and signature of consent	X						
Clinical data collection	X						
Randomization		X					
VAS	X			X		X	X
Oswestry Questionnaire	X			X		X	x

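### A normality check on the two per-mode VAS changes decides the primary analysis, and if it fails nothing planned estimates the paired mean difference on which the trial is sized

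*Combined protocol and SAP*

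**What the plan says.** The main-objective paragraph of A.7 defines the analysis variables: "two variables will be calculated for each patient that reflect the difference between the initial VAS minus the final VAS, one for each type". It continues: "We will calculate whether these differences conform to the Gaussian distribution". The only variables this can refer to are the two per-mode changes.

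If the check is passed, "the means with their standard deviations will be calculated for each of them", a paired t-test is run, and "these means will be adjusted for age and sex, establishing the possible statistical differences with a general linear model of repeated measures". If it is not passed, "the medians and the 25th and 75th percentiles will be calculated, obtaining the possible statistical differences by applying the Wilcoxon test". The t-test and the adjusted model appear only in the first branch. Neither branch names a confidence interval.

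The sample-size paragraph of A.7 states the target: "The main objective of the study is to establish a mean difference in the decrease in VAS". The calculation is described as "Using the formula for paired mean difference", with a difference of 1.9 points, SDs of 3.2 and 2.0 and a correlation of 0.5. The valuation criteria in the study overview agree: "The primary endpoint is the variation in VAS between the end of EMC mode and EME mode".

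Kolmogorov-Smirnov is named in the descriptive paragraph of A.7 and reasonably carries over to the primary analysis. The plan does not say whether it is corrected for an estimated mean and SD. A.7 also applies the VAS tests to the differences in the questionnaire scores, so the same rule governs the Oswestry comparison.

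**The concern.** There are two separate problems.

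First, the check is made on the wrong variables. A paired t-test requires nothing of either per-mode change alone; it uses only their within-patient difference. VAS is recorded at Visit 1 and not again before either stimulation period, so both changes share one baseline value, which cancels in that difference. The shape of the baseline distribution, restricted to 7 or more on a 0–10 scale, can therefore influence which analysis is run without affecting the comparison of modes.

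Second, the branches do not deliver the same quantity. In the first, the mean difference can at least be recovered from the two means. In the second, the outputs are two sets of medians and quartiles and a p-value, and none of them estimates a mean paired difference. The trial could then finish without a planned effect estimate to set against its own 1.9 points.

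**Working it through.** **Inputs from A.7.** Difference 1.9; SDs 3.2 and 2.0; correlation 0.5 (the plan calls it Spearman; it is used here as the ordinary correlation); 95% confidence, read as two-sided 0.05; power 80%; loss 20%.

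**The plan's own figure.**
- SD of the paired difference = √(3.2² + 2.0² − 2 × 0.5 × 3.2 × 2.0) = √7.84 = 2.80.
- Normal-approximation n = ((1.960 + 0.842) × 2.80 / 1.9)² = 17.05. Adding the small-sample term 1.960²/2 = 1.92 gives 18.97, so 19.
- Enrolment = 19 / 0.80 = 23.75, so 24.
- Exact paired-t power at n = 19 is 79.9%.

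The stated 19 and 24 reproduce, and they are sized on the mean paired difference.

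**What the t-test uses.** With baseline B and final scores F(EMC) and F(EME):

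(B − F(EME)) − (B − F(EMC)) = F(EMC) − F(EME).

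B drops out here but stays in each of the variables that are checked.

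**How often the check fails.** Simulation at n = 19, normal data, design SDs and correlation, 100,000 trials per case, Wilcoxon used if either change fails. The 5% critical distance is 0.197 with the correction for estimated parameters and 0.301 without it.

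| Quantity | Result |
|---|---|
| Check fails, corrected test | 9.7% (97% of these: one change passes, one fails) |
| Check fails, uncorrected test | 0.02% |
| Type I error, written rule / always t | 5.0% / 5.0% |
| Power at 1.9 points, written rule / always t | 79.6% / 79.8% |
| Trials where the conclusion differs | 0.2% (null), 0.4% (1.9 points) |

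**Bounded data (shapes assumed).** With baseline 7–10, final VAS 0–10, design SDs, correlation about 0.5 and beta-shaped final scores, the corrected test fails in 15–30% of trials, and in 60% in one case with many scores near zero. A simpler truncated-normal version gave about 12%. If scores are whole numbers, the range is 40–54%, and 77% in the near-zero case. The uncorrected test stays between about 0% and 6%. In the beta-shaped cases type I error is 4.7–5.7% for the rule against 4.7–5.4% for always t, power is 74–79% against 75–80%, and conclusions differ in at most 2.7% of trials.

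**What an unconditional estimate would give.** Standard error 2.80/√19 = 0.642; expected 95% CI half-width 2.101 × 0.642 = 1.35 points.

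**Why the gate should not be moved to the paired difference.** Take an assumed skewed difference with mean zero (75% N(0, 0.4) and 25% N(5, 1), centred; common part with SD 2.5). Rejection at nominal 5% is 7.8% for the written rule, 7.2% for always t and 12.2% with the gate on the paired difference. On skewed data, a correctly aimed gate sends the trial to a test of a different hypothesis.

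**The case against.** The strongest reply is that little is lost. Error rates, power and N barely change, conclusions almost always agree, and what is missing is an estimate and interval that one sentence could supply. This is right about error rates. It does not remove the point: when the rule is followed as written, the stated objective of establishing a mean difference can go unestimated.

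Second, the hypothesis paragraph in A.5 describes the primary endpoint as VAS after each mode compared with baseline, which matches the two variables that are checked. So the gate does follow one of the protocol's endpoint wordings. The t-test's assumption still concerns the paired difference, and so does the sample size.

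Third, a reader might infer that the plan has no rule when one change passes and the other fails. The wording does not support so strong a reading: the first branch requires that both fit, so Wilcoxon applies if either fails. This could be stated more clearly, but it can be resolved.

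Fourth, a reader might infer that the check will fail in most trials. The documents do not support that. The high rates need assumed shapes, and the highest also need whole-number scoring. Annex II prints a 0–10 grid, but A.6.4 describes a mark on a 10 cm line.

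**Conclusion.** The point stands as a defect in what is estimated. The normality check is applied to variables on which the paired t-test does not depend, and its failure branch contains no estimate of the mean difference that A.7 names and sizes. This follows from the text alone and needs no simulation.

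How often it matters cannot be fixed from the documents. With normal data at the design inputs it is about 10% of trials or about 0.02%, depending on a choice of Kolmogorov-Smirnov version that the plan leaves open. Anything higher rests on assumed distributions.

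A reader might infer that the two-stage rule inflates false positives, costs power or undermines the sample size. It does none of these to a material degree at the design inputs or in the bounded cases examined, and 19 evaluable and 24 enrolled remain correct for the stated assumptions. The change should be made, but the trial's validity does not hang on it.

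**What to change.** Remove the normality gate, and do not move it to the paired difference. Pre-specify the mean within-patient difference between EMC and EME in VAS decrease, with its 95% CI, as the primary result whatever the normality result. Take it from the paired t-test, or from the crossover model if a period term is added; this point does not settle whether one is needed. Keep the age- and sex-adjusted repeated-measures model as a stated secondary analysis. Report the Wilcoxon signed-rank test with the Hodges-Lehmann estimate and its CI, on the same within-patient difference, as a fixed sensitivity analysis. Apply the same scheme to the Oswestry scores.

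The cost is a few lines of A.7, with no new data and no change in N. The statistical downside is slightly less power than the written rule if the paired differences are heavy-tailed. For assumed t-distributed differences with SD 2.8, power is 80.6% for always t against 81.4% for the written rule at 5 df, and 85.9% against 88.2% at 3 df. The fixed Wilcoxon analysis would show such a case.
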